 - For patients undergoing systemic treatment (alone or in combination with targeted treatment): If on post-treatment follow-up imaging within 3-12 months, lymph nodes seen on CT or MRI decrease by more than 30% in short axis diameter and PSA declines by more than 50%.

- If PSA increases by more than 50% on systemic therapy, then a increase in the size of lesion by more than 20% will be considered a true positive lesion.
- In subjects with localized suspected lymph node(s) receiving targeted treatment without concomitant systemic treatment there are two ways to meet true positive disease:
- If the subject shows a decrease of PSA by greater than 50% after targeted treatment and the lymph node does not enlarge (change in size less than 20% or less than 3 mm increase in short axis diameter) [OR]
 - If on post-treatment follow-up imaging within 3-12 months, lymph nodes seen on CT or MRI decrease by more than 30% in short axis diameter (with a minimum of 3 mm in change in size)
- For untreated patients: If on follow-up imaging within 3-12 months, lymph nodes seen on CT or MRI increase by more than 20% in short axis diameter (with a minimum of 3 mm in change in size).
- (2) False positive:
- For patients undergoing systemic treatment (alone or in combination with targeted treatment): If on post-treatment follow-up imaging within 3-12 months, lymph nodes seen on CT or MRI increase by more than 20% in short axis diameter and PSA decreases by more than 50%.
- In subjects with localized suspected lymph node(s) receiving targeted treatment without concomitant systemic treatment there are two ways to meet false positive disease:
- If the subject does not demonstrate a decrease of PSA by greater than 50% after targeted treatment [OR]
 - If on post-treatment follow-up imaging within 3-12 months, lymph nodes seen on CT or MRI increase by more than 20% in short axis diameter (with a minimum of 3 mm in change in size)
- For untreated patients: If on follow-up imaging within 3-12 months, lymph nodes seen on CT or MRI decrease by more than 30% in short axis diameter (with a minimum of 3 mm in change in size).
- (3) If all regions in a patient/region do not meet criteria for either True positive or False positive disease, then the patient/region will be considered inevaluable for primary endpoint.
- ii) Visceral lesions (non-lymph node soft tissue or organ) will be assessed by change in size. ⁶⁸Ga-PSMA-11 positive visceral lesions will be considered:
- (1) True positive:

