- For patients undergoing systemic treatment (alone or in combination with targeted treatment): If on post-treatment follow-up imaging within 3-12

months, lesions seen on CT or MRI decrease by more than 30% in long axis diameter and PSA declines by more than 50%.

- If PSA increases by more than 50% on systemic therapy, then a increase in the size of lesion by more than 20% will be considered a true positive lesion.

- In subjects with localized suspected lesions(s) receiving targeted treatment without concomitant systemic treatment there are two ways to meet true positive disease:

- If the subject demonstrates a decrease of PSA by greater than 50% after targeted treatment [OR]
- If on post-treatment follow-up imaging within 3-12 months, lesions seen on CT or MRI decrease by more than 30% in long axis diameter (with a minimum of 3 mm in change in size)

- For untreated patients: If on follow-up imaging within 3-12 months, lesions seen on CT or MRI increase by more than 20% in long axis diameter (with a minimum of 3 mm in change in size).

(2) False positive:

- For patients undergoing systemic treatment (alone or in combination with targeted treatment): If on post-treatment follow-up imaging within 3-12 months, lesions seen on CT or MRI increase by more than 20% in long axis diameter and PSA decreases by more than 50%.

- In subjects with localized suspected lesions(s) receiving targeted treatment without concomitant systemic treatment there are two ways to meet false positive disease:

- If the subject does not demonstrate a decrease of PSA by greater than 50% after targeted treatment [OR]
- If on post-treatment follow-up imaging within 3-12 months, lesions seen on CT or MRI increase by more than 20% in long axis diameter (with a minimum of 3 mm in change in size)

- For untreated patients: If on follow-up imaging within 3-12 months, lesions seen on CT or MRI decrease by more than 30% in long axis diameter (with a minimum of 3 mm in change in size).

(3) If all regions in a patient/region do not meet criteria for either True positive or False positive disease, then the patient/region will be considered inevaluable for primary endpoint.

iii) ⁶⁸Ga-PSMA-11 positive bone lesions will be considered:

(1) True positive:

- If there was a corresponding positive sclerotic lesion on the CT portion of the ^{68}Ga -PSMA-11 PET or on a separate CT obtained ≤ 30 days before or after the PET/CT in the same location as the PSMA uptake.

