- If there is focal uptake seen in the same location as the PSMA uptake on the baseline bone scan performed within one month of ^{68}Ga -PSMA-11 PET.
- If there is a lesion noted in the same location as the PSMA uptake on the initial MRI performed within one month of ^{68}Ga -PSMA-11 PET.
- If within 12 months follow-up CT demonstrates development of sclerosis in the same location as the PSMA uptake.
- If within 12 months follow-up MRI demonstrates a new bone lesion in the same location as the PSMA uptake.
- If within 12 months follow-up bone scan demonstrates new focal uptake in the same location as the PSMA uptake.
- In subjects with localized suspected bone lesion(s) receiving targeted treatment without concomitant systemic treatment:
 - o If the subject demonstrates a decrease of PSA by greater than 50% after targeted treatment.

(2) False positive:

- In subjects with localized suspected bone lesion(s) receiving targeted treatment without concomitant systemic treatment:
 - o If the subject does not demonstrate a decrease of PSA by greater than 50% after targeted treatment with curative intent (ie non-palliative radiation).
- If ^{68}Ga -PSMA-11 positive bone lesions do not meet the criteria for true positive findings, and appropriate correlative and follow-up imaging was acquired.

(3) If bone lesions do not meet criteria for either true positive or false positive disease listed above, then the patient/region will be considered inevaluable for primary endpoint.

iv) ^{68}Ga -PSMA-11 positive prostate bed and prostate lesions will be considered:

(1) True positive:

- For patients undergoing systemic treatment (alone or in combination with targeted treatment): If on post-treatment follow-up imaging within 3-12 months, lesions seen on CT or MRI decrease by more than 30% in long axis diameter
- In subjects with localized suspected lesions(s) receiving targeted treatment without concomitant systemic treatment there are two ways to meet true positive disease:

- If the subject demonstrates a decrease of PSA by greater than 50% after targeted treatment [OR]
- If on post-treatment follow-up imaging within 3-12 months, lesions seen on CT or MRI decrease by more than 30% in long axis diameter (with a minimum of 3 mm in change in size)

- For untreated patients: If on follow-up imaging within 3-12 months, lesions seen on CT or MRI increase by more than 20% in long axis diameter (with a minimum of 3 mm in change in size).

(2) False positive:

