- For patients undergoing systemic treatment (alone or in combination with targeted treatment): If on post-treatment follow-up imaging within 3-12 months, lesions seen on CT or MRI increase by more than 20% in long axis diameter and PSA decreases by more than 50%.

- In subjects with localized suspected lesions(s) receiving targeted treatment without concomitant systemic treatment there are two ways to meet false positive disease:

- If the subject does not demonstrate a decrease of PSA by greater than 50% after targeted treatment [OR]
- If on post-treatment follow-up imaging within 3-12 months, lesions seen on CT or MRI increase by more than 20% in long axis diameter (with a minimum of 3 mm in change in size)

- For untreated patients: If on follow-up imaging within 3-12 months, lesions seen on CT or MRI decrease by more than 30% in long axis diameter (with a minimum of 3 mm in change in size).

(3) If the lesion does not meet criteria for either True positive or False positive disease, then the lesion will be considered inevaluable for primary endpoint.

c) Histopathology/Biopsy:

- i) ⁶⁸Ga-PSMA-11 positive findings are aimed to be confirmed by histopathology/biopsy if clinically feasible. Pathology performed 60 days before the PSMA PET will be available for correlation.
- ii) Histopathological procedures and biopsies will be performed as clinically indicated and as per institutional protocol.

(1) Positive Histopathology/Biopsy: Confirmed sites of metastatic or tumor involvement by histopathology/biopsy will be discussed with the responsible physician/surgeon.

- (a) True Positive: lesion is positive on targeted biopsy/surgical sampling and is read as positive on PSMA PET.
- (b) False Negative: lesion is positive on targeted biopsy/surgical sampling and is read as negative on PSMA PET.

- (2) **Negative Biopsy:** Patients with suspected tumor recurrence on ^{68}Ga -PSMA-11 PET with negative histopathology/biopsy will be handled as outlined below:
- (a) Lymph nodes:
- For patients undergoing nodal dissection: Patients will be rescanned with dedicated CT, MRI or a repeat ^{68}Ga -PSMA-11 PET to determine if the suspicious ^{68}Ga -PSMA-11 positive node was removed.
 1. If ^{68}Ga -PSMA-11 positive lymph node is still present, a repeat biopsy can be pursued if clinically feasible and applicable, or follow-up using imaging as described above will be performed.
 2. If the corresponding node was removed, then this will be considered a False Positive.

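### For prostate-bed lesions on systemic treatment, the true-positive rule omits both the PSA decline and the progression route that apply to nodes and visceral lesions, and no reason is given

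*Combined protocol and SAP*

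**What the plan says.** Section 8.3.2 b) sets out how follow-up imaging confirms or refutes a PET-positive lesion, by lesion type and treatment. For patients on systemic treatment, alone or with targeted treatment:

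- **Lymph nodes, i) (1).** True positive if "lymph nodes seen on CT or MRI decrease by more than 30% in short axis diameter and PSA declines by more than 50"%.
- **Visceral lesions, ii) (1).** True positive if "lesions seen on CT or MRI decrease by more than 30% in long axis diameter and PSA declines by more than 50"%.
- **Nodes and visceral lesions, second route.** Both lists add a progression clause in the same words: "If PSA increases by more than 50% on systemic therapy, then a increase in the size of lesion by more than 20"% is a true positive.
- **Prostate bed and prostate, iv) (1).** True positive if "lesions seen on CT or MRI decrease by more than 30% in long axis diameter". The item ends there, and no progression clause follows.
- **Prostate bed and prostate, iv) (2).** False positive if "lesions seen on CT or MRI increase by more than 20% in long axis diameter and PSA decreases by more than 50"%.

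A lesion that meets neither rule is inevaluable for the primary endpoint. Under 8.3.2 d), one true-positive region makes the patient a true positive even if other regions are inevaluable or false positive on imaging or clinical follow-up. A region that is false positive on pathology overrides this. Success requires two of three readers to reach 70% sensitivity at patient level.

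**The concern.** The prostate bed is one of the four regions in the primary objective. Within that region and treatment setting, a false positive needs a size change and a PSA change, while a true positive needs a size change alone. Two neighbouring lesion types in the same section use a stricter shrinkage rule and have an extra route to confirmation. The plan does not explain the difference.

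The PSA condition does real work here. Under section 8.1.2 and 8.3.2 b), follow-up images are measured by local readers who are unblinded and are told where the PET-positive lesions are. PSA is the part of the reference standard that does not depend on that reading. Pathology outranks imaging where it exists, but section 8.2.1 reports biopsy in only 19% of the first cohort and expects the rate to fall. Imaging and clinical follow-up will therefore decide many classifications. At stake are PPV and, through the one-region rule, the per-patient sensitivity on which success is judged.

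**Working it through.** **Step 1. Rules side by side.** Inputs are the systemic-treatment items of 8.3.2 b) i), ii) and iv). The table assumes no pathology.

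| Course on systemic treatment | Node | Visceral | Prostate bed |
|---|---|---|---|
| Shrinks >30%, PSA falls >50% | TP | TP | TP |
| Shrinks >30%, PSA flat, rising, or falling by 50% or less | inevaluable | inevaluable | **TP** |
| Grows >20%, PSA rises >50% | TP | TP | **inevaluable** |
| Grows >20%, PSA falls >50% | FP | FP | FP |
| Grows >20%, any other PSA course | inevaluable | inevaluable | inevaluable |
| Any smaller size change | inevaluable | inevaluable | inevaluable |

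The bed differs in two of the six rows, in opposite directions.

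**Step 2. Effect on the estimates.** Let T, F and P be the true-positive, false-negative and false-positive patients if the bed followed the visceral rule. Let a be the patients who become true positive only through the second row, and b those who lose true-positive status only through the third. Take the simple case in which these patients would otherwise be inevaluable. As written:

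- sensitivity = (T + a − b) / (T + a − b + F)
- PPV = (T + a − b) / (T + a − b + P)

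Both rise if a > b and fall if a < b. At patient level, a and b count only patients with no other true-positive region and no region that is false positive on pathology. The documents give no PSA response rate on systemic treatment, no share of patients on systemic treatment and no lesion-size changes, so neither a nor b can be derived.

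**Step 3. Scale near the success mark.** Let x = (a − b) / (T + F). At the plan's 70% mark, sensitivity becomes (0.70 + x) / (1 + x). The values of x below are assumed, because the documents give none:

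- x = +1%: 0.71 / 1.01 = 70.3%
- x = −1%: 0.69 / 0.99 = 69.7%
- x = +5%: 0.75 / 1.05 = 71.4%
- x = −5%: 0.65 / 0.95 = 68.4%

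Each net 1% of classified patients is worth about 0.3 percentage points. That matters only for a reader close to the mark.

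**Step 4. Which estimates can move.** Under 8.3.2 d) ii), a false-negative region requires positive pathology, and section 8.2.1 reports no false negatives on biopsy in the first cohort. If that recurs, F = 0 and per-region sensitivity is T / T = 100% whatever a and b are. Per-patient sensitivity can move, because 8.3.2 d) i) (4) also counts PET-negative patients with biochemical disease as false negatives, and section 8.2.1 expects 24% with no disease on PET. PPV can move at both levels.

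**The case against.** Several points on the other side are fair.

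- **The criteria are a guide.** Section 8.3.2 d) lets investigators deviate in individual patients and record it, and pathology takes precedence. This limits the damage of an inconsistent default but does not explain the default.
- **It may be a drafting slip.** The bed item ends without a full stop, so a clause may have been lost. This is weak evidence, since other items also lack one. A slip would still need the same correction, and the missing progression clause is a second, separate gap.
- **The regions already differ.** Bone lesions can be true positive on a baseline CT, bone-scan or MRI correlate with no PSA condition. Visceral and prostate-bed lesions on targeted treatment alone can qualify on a PSA fall alone or on shrinkage alone. The point therefore does not extend to a claim that the regions would otherwise be comparable.

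A reader might also infer three stronger things that the documents do not support.

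- **That the bed rule is singled out by lacking the 3 mm minimum, so that trivial changes in small lesions count as cancer.** No systemic-treatment size rule has that minimum, whether nodal, visceral or prostate bed, true or false positive. It appears only in the targeted-only and untreated rules. For shrinkage it would bind only below 10 mm (0.30 × 10 mm = 3 mm), and the visceral wording would not add it.
- **That sensitivity and PPV are biased upward overall.** The two omissions pull in opposite directions.
- **That 0.15 × 375 ≈ 56 patients are affected.** The 15% is an expected disease distribution and the 375 includes biopsied patients, for whom pathology decides. The affected group is confined to bed-positive patients on systemic treatment without pathology whose lesions follow one of the two discrepant courses.

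**Conclusion.** The inconsistency is real and specific. The prostate-bed systemic-treatment rule lacks a PSA condition that its nodal and visceral counterparts and its own false-positive rule all carry, and it lacks their progression route. Followed as written, two clinical courses are classified in the opposite way from nodes and visceral lesions, with no stated reason. Taken alone, the first omission can only raise PPV and per-patient sensitivity, and the second can only lower them. The net size and direction are unknown. The 0.3-point scaling in the working rests on an assumed net share and is not an estimate of bias. The wording should be reconciled before any case is classified against the reference standard, because the per-patient result decides success.

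**What to change.** In 8.3.2 b) iv) (1), bring the systemic-treatment item into line with the visceral one:

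- require a PSA decline above 50% together with long-axis shrinkage above 30%;
- add the clause that growth above 20% with a PSA rise above 50% on systemic therapy is a true positive.

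Bed lesions that shrink without the PSA decline then become inevaluable under iv) (3). If the difference is intended, state the reason instead and report how many bed lesions were classified by shrinkage alone.

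The cost is a wording change to the reference standard. It uses PSA values that the neighbouring rules already need and changes no patient care. The downside is that some bed lesions become inevaluable, while others become evaluable through the progression clause. A minimum absolute size change is a separate decision. If one is wanted, consider it for nodal, visceral and prostate-bed systemic-treatment rules together.

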2.2 Secondary

- PPV on a per-patient and per-region-basis (Table 1) of ^{68}Ga -PSMA-11 PET for detection of tumor location confirmed by histopathology/biopsy, clinical and conventional imaging follow-up.
- Sensitivity and positive predictive value (PPV) on a per-patient and per-region-basis (Table 1) of ^{68}Ga -PSMA-11 PET for detection of tumor location confirmed by histopathology/biopsy.
- Detection rates on a per-patient basis of ^{68}Ga -PSMA-11 PET stratified by PSA value (0.2 - <0.5, 0.5 - <1.0, 1.0 - <2.0, 2.0 - <5.0, \geq 5.0). Detection rate will also be stratified by history of prostatectomy, radiation or both; as well as by whether the patient is on androgen deprivation therapy (ADT).
- Impact of ^{68}Ga -PSMA-11 PET on clinical management in BCR patients.
- Inter-reader reproducibility.
- Safety, as characterized by CTCAE 4.03.

3 Study Design

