Of our first cohort of patients, 19% of patients underwent biopsy after a positive PSMA PET imaging. Based on biopsy results there was 100% sensitivity and 87% specificity. There were no True Negatives or False Negatives on biopsy. Imaging follow-up is not complete for our first study so we cannot estimate the percent of patients that will have imaging follow-up, but it appears that roughly 15 to 20% of patients will have imaging follow-up. Consistent with our second protocol, we anticipated that the sensitivity for the four regions and for all regions combined using conventional imaging ranges from 30-60%. An overall sensitivity for ^{68}Ga -PSMA-11 PET of at most 50% will be considered as unacceptably low. Hence, the null hypothesis that the sensitivity is at most 50% will be tested against the alternative hypothesis that the sensitivity is greater than 50%. It is hypothesized that ^{68}Ga -PSMA-11 PET imaging on the per-region and per-patient basis will substantially increase the sensitivity for the four regions to at least 70%. A sample size of 75 true positives is required for rejecting the null hypothesis that the sensitivity is at most 50% with 90% power at the one-sided 0.01 ($=0.05/5$ – a Bonferroni adjustment for evaluating the sensitivity for the four regions and for all regions combined) significance level, assuming an average regions specific prevalence of 20%. Although 19% of patients underwent biopsy and 15% of patients have imaging follow-up, we anticipate that the biopsy rate will fall in this study as referring clinicians become more comfortable with the imaging results. Therefore, we will combine imaging and biopsy follow-up in the primary aim, and will require 375 with both imaging and/or biopsy follow-up in order to power the analysis at a per region level. Assuming a prevalence rate of 20% for disease in each individual region, a total sample size of 1,500 patients is required. In summary, the proposed target accrual of 1,500 patients (375 with biopsies or imaging follow-up) will provide adequate power for detecting the anticipated improvement in the sensitivity for both the per-patient and per-region based ^{68}Ga -PSMA-11 PET imaging. However, a sample size of 107 patients with biopsies/follow-up in total is sufficient for detecting the anticipated improvement in sensitivity when evaluating per-patient based sensitivity.

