8.3.3 Analysis of Secondary Endpoints

1. PPVs on a per-patient and per-region-basis of ^{68}Ga -PSMA-11 PET for detection of tumor location confirmed by histopathology/biopsy, clinical and conventional imaging follow-up will be calculated and reported along with the corresponding two-sided 95% confidence intervals. The confidence intervals will be constructed using the Wilson score method. PPV will be reported for each of the three blinded readers independently.
2. Sensitivity and PPVs on a per-patient and per-region basis of ^{68}Ga -PSMA-11 PET for detection of tumor location confirmed by histopathology/biopsy will be summarized in tabular format. Ninety-five percent confidence intervals of sensitivity, specificity, NPV and PPV will be calculated using the Wilson score method. These will be reported for each of the three blinded readers.
3. Detection rates on a per-patient basis of ^{68}Ga -PSMA-11 PET stratified by PSA value (0.2 - <0.5, 0.5 - <1.0, 1.0 - <2.0, 2.0 - <5.0, ≥ 5.0) will be summarized in tabular format and compared between PSA strata using chi-square analysis. Detection rate will also be stratified by history of prostatectomy, radiation or both; as well as by whether the patient is on androgen deprivation therapy (ADT). We will use local interpretations for this analysis.
 - a. Detection rate is defined as number of patients with PSMA positive disease, independent of pathology, imaging or clinical follow-up. A detection rate will be reported for each reader independently stratified by PSA.
4. The impact of ^{68}Ga -PSMA-11 PET on clinical management in BCR patients will be evaluated using descriptive statistics.
5. Inter-reader reproducibility for positivity at the patient level and region level will be reported using the Fleiss' Kappa test for multiple readers. We will use the three blinded reads for this analysis.
6. Safety will be reported descriptively as rates of patient reported adverse events. Additionally, adverse events will be characterized and quantified by CTCAE 4.03.

9 Study Management

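### Histopathology-only sensitivity is biased upward because biopsies are aimed at PET-positive findings, and the false-negative rules for this endpoint are contradictory or unstated

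*Combined protocol and SAP*

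**What the plan says.** **Endpoint.** Section 2.2 lists sensitivity and PPV, per patient and per region, against histopathology alone. Section 8.3.3 item 2 says these measures "for detection of tumor location confirmed by histopathology/biopsy will be summarized in tabular format", with Wilson 95% intervals for each of the three blinded readers. It describes no adjustment for which sites are sampled.

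**Who is sampled.** Section 8.3.2 c says that, on PET, "positive findings are aimed to be confirmed by histopathology/biopsy if clinically feasible". It continues: "Histopathological procedures and biopsies will be performed as clinically indicated and as per institutional protocol". It also says: "Pathology performed 60 days before the PSMA PET will be available for correlation". A pathology false negative is defined there as a sampled, tissue-positive lesion that is read as PET-negative.

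**Earlier cohort.** Section 8.2.1 reports that "19% of patients underwent biopsy after a positive PSMA PET imaging" and then: "Based on biopsy results there was 100% sensitivity and 87% specificity. There were no True Negatives or False Negatives on biopsy".

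**Counting rules (8.3.2 d).**
- A region or patient can be a pathology false negative only if it has no true-positive or false-positive lesion.
- Regions with no PSMA-positive disease are left out of the region analysis, yet false-negative regions are defined in the same item.
- A patient with a negative PET and biochemical disease is counted as a false negative.

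Item 2 of 8.3.3 does not say which of these rules govern the histopathology-only figures.

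**The concern.** Sensitivity is the share of diseased sites that PET finds, so its denominator needs the diseased sites that PET misses. Here tissue is sought mainly where PET is positive, and missed disease enters only by chance routes. The ratio TP/(TP+FN) then reflects sampling practice as well as the tracer. A Wilson interval around it covers sampling error only, so a large number of biopsies makes a biased figure look precise. PPV from the same biopsies does not have this defect, because its denominator is PET-positive findings.

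Section 1.1 intends the data for an NDA. The issue also touches the primary claim. The opening of 8.2.1 and the analysis population in 8.3.1 describe the primary aim in terms of histopathology, whereas 2.1, the opening of 8.3.2 and the later part of 8.2.1 combine pathology with follow-up. The 70% success rule in 8.3.2 names pathology correlation among its case sets.

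**Working it through.** **1. The plan's own figure.** With no false negatives on biopsy, sensitivity = TP/(TP+0) = 100% for any TP above zero. So the earlier cohort's 100% is reproduced, but it would be 100% whatever the true sensitivity. The accompanying 87% cannot be a specificity, because TN/(TN+FP) is 0 when TN = 0 and FP > 0. It is read below as PPV, which is an assumption.

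**2. Effect of selective sampling.** Let S be true sensitivity, v1 the share of PET-positive disease that gets pathology, and v0 the same share for PET-negative disease.

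Apparent sensitivity = S·v1 / [S·v1 + (1−S)·v0]

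Inputs:
- v1 = 19% if the 19% in 8.2.1 is a share of PET-positive patients. If it is a share of all patients, and 100 − 24 = 76% are PET-positive (8.2.1), then v1 = 0.19/0.76 = 25%. Either way, the patient-level rate is assumed to apply to PET-positive disease.
- v0 is not given in the documents. The range 0 to 5% is assumed.
- S = 50% is the null value in 8.2.1 and 70% the target. S = 30% is the low end of the range that 8.2.1 gives for conventional imaging, used here as a poor-performance case.

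| True S | v1 | v0 = 0 | v0 = 1% | v0 = 2% | v0 = 5% |
|---|---|---|---|---|---|
| 30% | 19% | 100% | 89.1% | 80.3% | 62.0% |
| 30% | 25% | 100% | 91.5% | 84.3% | 68.2% |
| 50% | 19% | 100% | 95.0% | 90.5% | 79.2% |
| 50% | 25% | 100% | 96.2% | 92.6% | 83.3% |
| 70% | 19% | 100% | 97.8% | 95.7% | 89.9% |

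Example: S = 50%, v1 = 19%, v0 = 1% gives 0.095/(0.095 + 0.005) = 95.0%.

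The apparent figure equals S only when v0 = v1. A tracer with S = 30% appears at 70% or better unless v0 exceeds 0.3·v1·0.3/(0.7·0.7), which is 3.5% for v1 = 19% and 4.6% for v1 = 25%.

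**3. What the interval would show.** With 1,500 × 0.19 × 0.87 = 248 true positives and no false negatives, the Wilson lower limit is 248/(248 + 1.96²) = 98.5%. The interval would be 98.5 to 100% even if S were 50%.

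**4. Region level.** If regions without PSMA-positive disease are dropped, no region can be a false negative, so FN = 0 and regional sensitivity is 100%. If the false-negative region definition in the same item governs, FN can exceed zero. The two statements cannot both be followed.

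**5. Patient level.** If PET-negative patients with biochemical disease enter this endpoint, FN = 1,500 × 0.24 = 360.
- 19% of all patients biopsied: TP = 248, sensitivity = 248/(248 + 360) = 41%.
- 19% of PET-positive patients biopsied: TP = 1,500 × 0.76 × 0.19 × 0.87 = 188, sensitivity = 188/(188 + 360) = 34%.

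If the rule does not enter, step 2 applies. The plan does not say which.

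**The case against.** The strongest reply is that the plan does allow pathology false negatives. It defines them for lesions, regions and patients. It admits tissue taken in the 60 days before PET, which the PET result cannot have selected, and it foresees nodal dissection. Item 2 of 8.3.3 also asks for specificity and NPV, which need PET-negative tissue. Scoring is by blinded central readers, so a biopsy-proven lesion that was positive on the local read and is missed centrally counts as a false negative. The biochemical rule could push the patient-level figure well below 100%. The endpoint is secondary and descriptive.

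Much of this stands. A reader might infer that the sensitivity is 100% by construction, that the earlier cohort demonstrates this, or that the endpoint cannot measure sensitivity at all. The documents do not support those readings. False negatives have several routes in. Zero false negatives in the earlier cohort fits selective sampling but also fits a truly high sensitivity, and its biopsy count is not given. A subset not selected by PET could yield a usable estimate. The case-set list in the 70% rule can also be read as describing one evaluable group rather than three separate ways to succeed.

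The replies do not remove the bias. The routes are incidental, and nothing makes v0 approach v1. A central miss of a locally positive lesion mainly measures agreement between readers; it says nothing of disease that both reads missed. In a dissection with one true-positive node, missed nodes in the same region are not counted. If the biochemical rule applies, the figure depends on how many patients are biopsied, which is no better.

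**Conclusion.** The concern holds in this form: histopathology-only sensitivity, as planned, is subject to partial-verification bias. Among sampled lesions the bias is upward whenever PET-negative disease is verified less often than PET-positive disease, and the plan does nothing to equalise the two. Its size rests on the assumed v0: for a true sensitivity of 50%, it is 45 to 50 points at v0 = 0 to 1% and about 29 to 33 points at v0 = 5%.

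The upward direction is not established for every version of the endpoint. The region figure is 100% by definition only under the literal exclusion rule. The patient figure falls to about 34 to 41% if the biochemical rule applies, taking the 87% as PPV. That the same endpoint can read about 34% or 100% depending on unstated rules is itself a reason to amend. The primary aim is affected only if the pathology-only set can satisfy the 70% rule, which the present wording does not exclude.

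**What to change.** 1. In 8.3.3 item 2, make PPV the main measure for PET-directed biopsies, and do not present sensitivity from that set as an estimate of tracer sensitivity.
2. Report histopathology sensitivity in specimens not selected by PET (pathology from the 60 days before PET, template dissections). Count every sampled region, PET-positive or not, and give the number and source of pathology-verified PET-negative units. Add a case report form flag: sampling directed by PET, yes or no.
3. Correct 8.3.2 d so that pathology-positive, PET-negative regions count as false negatives, and state that the biochemical false-negative rule does not enter the histopathology-only endpoint.
4. Reconcile the opening of 8.2.1, 8.3.1 and the 70% rule in 8.3.2 with 2.1 and the later text of 8.2.1, so that the rule applies to the combined pathology and follow-up set and cannot be met by the pathology-only set.

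Cost: a protocol amendment with PRC and CHR approval (9.4), coordination with the sites whose endpoints were aligned for pooling (1.1), and one data flag. The sensitivity subset will be small and its interval wide. It is also not a random sample, since that tissue was taken for other clinical reasons, and the report should say so.
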